3.2.3 Rationale for Endpoints

MEDI9929 is being developed as a controller therapy for subjects with inadequately controlled, severe asthma with the aim to achieve and maintain asthma control for prolonged periods. The GINA guidelines (GINA, 2012) recommend that the assessment of asthma control should not only include the control of clinical manifestations (symptoms, sleep disturbance, limitation of daily activity, impaired lung function, and use of rescue medication) but also the control of expected future risk including the incidence of asthma exacerbations. The endpoints chosen for this study provide the opportunity to assess the impact of MEDI9929 on these different aspects of asthma control.

Asthma exacerbations are important because they constitute the greatest medical risk to patients, are a cause of anxiety to patients and their families, result in the greatest stress on healthcare providers, and generate the greatest cost to the health care systems (Lane et al, 2006). It is therefore important to establish whether the use of MEDI9929, in addition to GINA Step 4 or 5 standard of care, is associated with a reduction in the annual asthma exacerbation rate (see Section 4.3.1.1 for definition of asthma exacerbation) when compared to placebo in addition to GINA Step 4 or 5 standard of care. The rate of asthma exacerbations has therefore been selected as the primary efficacy variable. Additional measures associated with asthma exacerbations are also being examined to determine effect. These include hospitalizations related to asthma exacerbations (ie, severe asthma exacerbations), time to first asthma exacerbation, and the proportion of subjects with one or more asthma exacerbation/severe asthma exacerbation.

The secondary endpoints include other established measures of asthma control (eg, pulmonary function, asthma symptoms, and rescue asthma medication use) and quality of life, which together with the safety and tolerability of MEDI9929 will be critical in establishing the potential clinical utility of MEDI9929.

27 of 113 Template 16.0

Additional secondary and exploratory endpoints in the study will help identify the optimal dose and dose regimen to be used in future studies, along with the subpopulation(s) that is likely to respond to treatment with MEDI9929. The asthma subpopulations include, but are not limited to: eosinophilic and non-eosinophilic; Th2 high/low (Corren et al, 2011); FE_{NO} high/low; periostin high/low; current post-BD FEV₁ reversibility; allergic and non-allergic; and markers of TSLP pathway activation (to be determined). A similar approach has been used in a recent study exploring the effect of omalizumab in subsets of asthmatics with and without evidence of Th2-type inflammation (Hanania et al, 2013).

4 MATERIALS AND METHODS

4.1 Subjects

4.1.1 Number of Subjects

Approximately 552 subjects will be randomized in a 1:1:1:1 ratio to receive one of 3 doses of MEDI9929 or placebo. Approximately 138 subjects will be randomized to each treatment arm.

Subjects will be stratified as described in Section 3.1.1. The target enrollment for each stratification factor is as follows:

- Study sites (non-Japanese or Japanese) Japanese population will account for approximately 15% of the targeted enrollment of 552 subjects.
- Blood eosinophil count at least 50% of all subjects randomized will have blood eosinophil count ≥ 250 cells/μL.
- ICS dose level at least 40% of all subjects randomized will be taking high-dose ICS and/or maintenance OCS.

In addition to the target enrollment for each stratification factor, at least 50% of subjects in the study will demonstrate current post-BD FEV₁ reversibility.

4.1.2 Inclusion Criteria

Subjects must meet *all* of the following criteria:

- 1. Age 18 through 75, inclusive at the time of Visit 1 (Week -5).
- 2. Written informed consent and any locally required authorization (eg, Health Insurance Portability and Accountability Act [HIPAA] in the USA, European Union [EU] Data Privacy Directive in the EU) obtained from the subject/legal representative prior to performing any protocol-related procedures, including screening evaluations.

- 3. Body mass index between 18-40 kg/m², inclusive and weight \geq 40 kg at Visit 1 (Week -5).
- 4. Documented physician-diagnosed asthma for at least 12 months prior to Visit 1 (Week -5) and post-BD reversibility of FEV₁ ≥ 12% and ≥ 200 mL during screening. Documented history of post-BD FEV₁reversibility in the past 12 months will be accepted in place of reversibility during screening.
- 5. For subjects 65 years or older at Visit 1 (Week -5) a chest x-ray (CXR) taken during the screening period or a CXR or chest computed tomography—scan within 12 months prior to Visit 1 (Week -5)—that, according to the investigator, is normal for an asthmatic subject and excludes significant alternative respiratory disease is required.
- 6. Subjects must have received a physician-prescribed asthma controller regimen with medium- or high-dose ICS plus LABA for at least 6 months prior to Visit 1 (Week -5), and the dose of ICS must be stable for at least 15 days prior to Visit 1 (Week -5) and throughout the screening/run-in period.
 - $^{\circ}$ To be classified as being on high-dose ICS, the subjects will be on a total daily dose of > 500 µg fluticasone dry powder inhaler (DPI), or a total daily dose of > 440 µg fluticasone metered dose inhaler (MDI) or equivalent.
 - To be classified as being on medium-dose ICS, the subjects will be on a total daily dose (sum of all ICS) of 250 to 500 μg fluticasone DPI or a total daily dose of 220 to 440 μg fluticasone MDI or equivalent.
 - Equivalent ICS doses will be based upon the GINA guidelines (GINA, 2012), shown in Appendix 5.
- 7. If on asthma controller medications in addition to ICS plus LABA, the dose of the other asthma controller medications (leukotriene receptor inhibitors, theophylline, secondary ICS, LAMA, cromones, or maintenance oral prednisone or equivalent up to a maximum of 10 mg daily or 20 mg every other day for the maintenance treatment of asthma) must be stable for at least 15 days prior to Visit 1 (Week -5).
- 8. Subjects must have a morning pre-BD FEV₁ value of \geq 40% and \leq 80%, predicted at 2 Screening Visits. The first time must be at either Visit 1 (Week -5) or Visit 2 (Week -4), and the second time must be at Visit 3 (Week -1).
- 9. Subjects must have an ACQ-6 score of ≥ 1.5 twice during screening. The first time must be at Visit 1 (Week -5). The second time may be at either Week -2 (taken from home recording on the electronic patient-reported outcome [ePRO] device) or at Visit 3 (Week -1).
- 10. At Visit 4 (Week 0, Day 1), subjects must have at least one of the following over the previous 7 days from the ePRO device:
 - > 2 days with a daytime or nighttime symptoms score \ge 1 (Asthma Daily Diary); or
 - \circ ≥ 1 awakening due to asthma requiring rescue medication use; or
 - Rescue/reliever short-acting β2 agonist (SABA) use > 2 days.
- 11. Subjects must have a documented history of at least 2 asthma exacerbation events OR at least 1 severe asthma exacerbation resulting in hospitalization (admission to the hospital for at least 24 hours) within the 12 months prior to Visit 1 (Week -5). To qualify as an asthma exacerbation event, administration of a burst of systemic corticosteroids for at

least 3 consecutive days must have been required for the treatment of the asthma exacerbation, or the asthma exacerbation resulted in an emergency department (ED) visit which required systemic corticosteroids for at least 3 consecutive days or hospitalization. For subjects receiving maintenance OCS, a temporary doubling of the stable existing maintenance dose for at least 3 days qualifies.

- 12. If on allergen-specific immunotherapy subjects must be on a maintenance dose and schedule for at least 2 months prior to Visit 1 (Week -5).
- 13. Subjects must meet the all of following criteria at Visit 4 (Week 0, Day 1) prior to randomization:
 - Subjects must demonstrate acceptable inhaler, peak flow meter, and spirometry techniques during screening/run-in period (from Visit 2 to Visit 4).
 - Subjects must demonstrate ≥ 70% compliance with usual asthma controller ICS/LABA during the screening/run-in period (from Visit 2 to Visit 4) based on the Asthma Daily Diary.
 - Subjects must demonstrate ≥ 80% compliance with required use of the ePRO device; 80% compliance is defined as completing the Asthma Daily Diary for any 8 mornings and any 8 evenings in the previous 10 days of the screening/run-in period.
- 14. Females of childbearing potential who are sexually active with a nonsterilized male partner must use a highly effective method of contraception from the time informed consent is obtained and must agree to continue using such precautions through Week 64 of the study; cessation of contraception after this point should be discussed with a responsible physician. Periodic abstinence, the rhythm method, and the withdrawal method are not acceptable methods of contraception.
 - Females of childbearing potential are defined as those who are not surgically sterile (ie, bilateral tubal ligation, bilateral oophorectomy, or complete hysterectomy) or postmenopausal (defined as 12 months with no menses without an alternative medical cause).
 - A highly effective method of contraception is defined as one that results in a low failure rate (ie, less than 1% per year) when used consistently and correctly. The acceptable methods of contraception are described in Table 4.1.2-1.

Table 4.1.2-1 Highly Effective Methods of Contraception

	Barrier Methods		Hormonal Methods
•	Male condom plus spermicide when combined	•	Implants
	with other methods	•	Hormone shot or injection
•	Copper T intrauterine device	•	Combined pill
•	Levonorgesterel-releasing intrauterine system	•	Minipill
	(eg, Mirena [®]) ^a	•	Patch

This is also considered a hormonal method.

4.1.3 Exclusion Criteria

Any of the following would exclude the subject from participation in the study:

- 1. Diagnosis of vocal cord dysfunction, reactive airways dysfunction syndrome, hyperventilation and panic attacks, or other mimics of asthma.
- 2. An established diagnosis of occupational asthma.
- 3. Current smokers or subjects with a smoking history of ≥ 10 pack years (number of pack years = number of cigarettes per day/20 × number of years smoked). Former smokers with < 10 pack years must have stopped for at least 6 months to be eligible.
- 4. Previous medical history or evidence of an uncontrolled intercurrent illness that in the opinion of the investigator and/or medical monitor may compromise the safety of the subject in the study or interfere with evaluation of the investigational product or reduce the subject's ability to participate in the study. Subjects with well-controlled comorbid disease (eg, hypertension, hyperlipidemia, gastroesophageal reflux disease) on a stable treatment regimen for 15 days prior to Visit 1 (Week -5) are eligible.
- 5. Any concomitant respiratory disease that in the opinion of the investigator and/or medical monitor will interfere with the evaluation of the investigational product or interpretation of subject safety or study results (eg, chronic obstructive pulmonary disease, cystic fibrosis, pulmonary fibrosis, bronchiectasis, allergic bronchopulmonary aspergillosis, Churg-Strauss syndrome).
- 6. Any clinically relevant abnormal findings in hematology, clinical chemistry, or urinalysis (laboratory results from Visit 1 [Week -5] and Visit 3 [Week -1]), physical examination, vital signs during the screening/run-in period, which in the opinion of the investigator, may put the subject at risk because of his/her participation in the study, or may influence the results of the study, or the subject's ability to participate in the study.
- 7. Evidence of active liver disease, including jaundice or aspartate transaminase, alanine transaminase, or alkaline phosphatase greater than twice the upper limit of normal (laboratory results from Visit 1 [Week -5] and Visit 3 [Week -1]).
- 8. History of cancer:
 - Subjects who have had basal cell carcinoma or in situ carcinoma of the cervix are eligible to participate in the study provided that curative therapy was completed at least 12 months prior to Visit 1 (Week -5).
 - Subjects who have had other malignancies are eligible provided that curative therapy was completed at least 5 years prior to Visit 1 (Week -5).
- 9. Acute upper or lower respiratory infections requiring antibiotics or antiviral medications within 15 days prior to Visit 1 (Week -5), during the screening/run-in period, or at Visit 4 (Week 0, Day 1).
- 10. Evidence of a clinically significant infection or receiving treatment with antibiotics or antiviral medications at Visit 4 (Week 0, Day 1).
- 11. A helminth parasitic infection diagnosed within 24 weeks of Visit 1 (Week -5) that has not been treated, or has not responded to standard of care therapy.

31 of 113 Template 16.0

- 12. Known history of active tuberculosis (TB) or a positive QuantiFERON[®]-tuberculosis Gold (QFT-G) test for TB during screening. Subjects with a positive or indeterminate QFT-G result may be enrolled if they have ALL of the following:
 - No symptoms of TB: productive, prolonged cough (> 3 weeks); coughing up blood; fever; night sweats; unexplained appetite loss; unintentional weight loss.
 - No known exposure to a case of active TB after most recent prophylaxis (prophylaxis required only if positive).
 - No evidence of active TB on chest radiograph within 3 months prior to the first dose of investigational product.

Subjects with an indeterminate QFT-G result will have repeat QFT-G testing during the study (Weeks 12, 28, 40, and 52).

- 13. Positive hepatitis B surface antigen, or hepatitis C virus antibody serology at screening, or a positive medical history for hepatitis B or C. Subjects with a history of hepatitis B vaccination without history of hepatitis B are allowed to enroll.
- 14. A positive human immunodeficiency virus (HIV) test at screening or subject taking antiretroviral medications, as determined by medical history and/or subject's verbal report.
- 15. History of sensitivity to any component of the investigational product formulation or a history of drug or other allergy that, in the opinion of the investigator or medical monitor contraindicates their participation.
- 16. History of anaphylaxis to any biologic therapy.
- 17. History of documented immune complex disease (Type III hypersensitivity reactions) to mAb administration.
- 18. History of any known primary immunodeficiency disorder excluding asymptomatic selective immunoglobulin A or IgG subclass deficiency.
- 19. Systemic corticosteroid burst including taper within 15 days prior to Visit 1 (Week -5) or during the screening/run-in period.
- 20. Use of 5-lipoxygenase inhibitors (eg, zileuton) within 15 days prior to Visit 1 (Week -5).
- 21. Use of immunosuppressive medication (eg, methotrexate, troleandomycin, oral gold, cyclosporine, azathioprine, intramuscular long-acting depot corticosteroid, or any experimental anti-inflammatory therapy) within 3 months prior to Visit 1 (Week -5). Chronic oral prednisone or equivalent up to a maximum of 10 mg daily or 20 mg every other day for the maintenance treatment of asthma is permitted.
- 22. Receipt of any of the following within 30 days prior to Visit 1 (Week -5)
 - Immunoglobulin or blood products, or
- 23. Receipt of any investigational nonbiologic agent within 30 days or 5 half-lives prior Visit 1 (Week -5), whichever is longer.
- 24. Receipt of any marketed (including omalizumab) or investigational biologic agent within 4 months or 5 half-lives prior to Visit 1 (Week -5), whichever is longer.
- 25. Pregnant, breastfeeding or lactating females
- 26. History of chronic alcohol or drug abuse within 12 months prior to Visit 1 (Week -5).

- 27. Planned surgical procedures requiring general anesthesia or in-patient status for > 1 day during the conduct of the study.
- 28. Unwillingness or inability to follow the procedures outlined in the protocol to Week 64.
- 29. Concurrent enrollment in another clinical study involving an investigational treatment.
- 30. Receipt of any oral or ophthalmic β-adrenergic antagonists (eg, propranolol) within 15 days prior to Visit 1 (Week -5).
- 31. Receipt of the Th2 cytokine inhibitor suplatest within 15 days prior to Visit 1 (Week-5).
- 32. Receipt of any live or attenuated vaccines within 15 days prior to Visit 1 (Week -5).

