Spirometry (pre-BD)	X		X		X		X				X		
Spirometry (post-BD)	X												
Randomize	X												
Investigational product administration ^e	X	X	X	X	X	X	X	X	X	X	X	X	X

ACQ -6 = Asthma Control Questionnaire, omitting FEV₁; ADA = anti-drug antibodies; AE = adverse event; AQLQ(S)+12 = Asthma Quality of Life Questionnaire (Standardised); D = Day; DNA = deoxyribonucleic acid; ECG = electrocardiogram; ePRO = electronic patient reported outcome; EQ-5D-5L = European Quality of Life - 5 Dimensions 5 Level Version; FEIA = fluorescence enzyme immunoassay; FE_{NO} = fraction of exhaled nitric oxide; FEV₁ = forced expiratory volume in one second; HRU = healthcare resource utilization; IgE = immunoglobulin E; PK = pharmacokinetic(s); post-BD = post-bronchodilator; pre-BD = pre-bronchodilator; PRO = patient reported outcome; QFT-G = QuantiFERON etuberculosis Gold; SAE = serious adverse event; WPAI+CIQ = Work Productivity and Activity Impairment Questionnaire plus Classroom Impairment Questions

The PRO assessments include Asthma Daily Diary, home peak flow, ACQ-6, AQLQ(S)+12, EQ-5D-5L, WPAI+CIQ. The assessment schedules are programmed into the ePRO device. Subjects will be triggered to complete the appropriate questionnaires/assessments at the appropriate intervals (eg, daily, weekly, biweekly)

Vital signs will be done prior to investigational product administration, 60 and 120 minutes (± 5 minutes) after the first 5 doses of investigational product are administered, and 60 minutes (± 5 minutes) after the sixth and subsequent doses of investigational product are administered. If the subject is not stable, vital signs should be monitored at least hourly until the subject is discharged from the study center

Table 4.2.2-1 Schedule of Treatment Period Study Procedures Week 0 to Week 24

Study Period		Treatment Period											
Visit Number	4	5	6	7	8	9	10	11	12	13	14	15	16
Study Week	0 (Day 1)	2	4	6	8	10	12	14	16	18	20	22	24
Procedure/Visit Window	± 3 D	± 3 D	± 3 D	± 3 D	± 3 D	± 3 D	± 3 D	± 3 D	± 3 D	± 3 D	± 3 D	± 3 D	± 3 D

^c The ECG is completed in triplicate until site notified by sponsor that the ECG sub-study is complete

d Only subjects with an indeterminate QFT-G result at screening

^e There must be ≥ 7 days between doses.

Table 4.2.2-2 Schedule of Treatment Period Study Procedures - Week 26 to Week 52

Study Period		Treatment Period												
Visit Number	17	18	19	20	21	22	23	24	25	26	27	28	29	EDV30
Study Week	26	28	30	32	34	36	38	40	42	44	46	48	50	52

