4.3.4.1 Tuberculosis Testing

All subjects will have the QFT-G test, which will be performed by the central clinical laboratory.

If a subject has an indeterminate QFT-G test at screening, the chest x-ray shows no evidence of active TB, there are no signs or symptoms of active TB, there is no recent contact with

anyone with active TB, and there is no history of latent (unless diagnosed within the 3 years prior to screening with documentation of completion of appropriate treatment) or active TB, the subject may be randomized and will have additional QFT-G testing performed at Weeks 12, 28, 40, and 52. Additionally, if in the opinion of the principal investigator and after discussion with the medical monitor, an expert specializing in TB may be consulted prior to randomization. If, during the study, a subject is determined to have a positive QFT-G result, the local country guidelines should be consulted for acceptable anti-TB treatment regimens. If no local guidelines exist for immunocompromised individuals, then USA guidelines must be followed.

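### For an indeterminate screening QFT-G, exclusion criterion 12 and Section 4.3.4.1 set different entry conditions on latent TB history and on exposure

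*Protocol*

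**What the plan says.** Protocol Section 4.1.3, criterion 12, excludes a known history of active TB or a positive screening QFT-G, and then opens an exception: "Subjects with a positive or indeterminate QFT-G result may be enrolled if they have ALL of the following". The conditions are absence of TB symptoms, an exposure condition ("No known exposure to a case of active TB after most recent prophylaxis (prophylaxis required only if positive"), and an imaging condition ("No evidence of active TB on chest radiograph within 3 months prior to the first dose of investigational product"). Latent TB is not mentioned.

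Protocol Section 4.3.4.1 covers much of the same ground under the opening words "If a subject has an indeterminate QFT-G test at screening". It allows randomization when the chest x-ray is clear, there are no signs or symptoms, there has been no recent contact with an active case, and a history condition is met: "there is no history of latent (unless diagnosed within the 3 years prior to screening with documentation of completion of appropriate treatment) or active TB". It mentions a positive QFT-G only as something found during the study. It also provides for optional consultation of a TB specialist before randomization, after discussion with the medical monitor.

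Both sections prescribe repeat QFT-G at Weeks 12, 28, 40 and 52 for subjects with an indeterminate result. The footnote to the treatment-period schedule tables in Section 4.2.2 agrees: "Only subjects with an indeterminate QFT-G result at screening".

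**The concern.** Each passage reads as a complete rule: the first says when such a subject may be enrolled, the second when the subject may be randomized. Neither refers to the other. A site working from criterion 12 and a site working from the TB section can reach different decisions on the same person.

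This is a safety entry criterion. Section 1.5 names serious infection as a potential risk of the product, and Section 5.2 makes confirmed TB needing treatment a serious adverse event. With about 110 centers planned (Section 3.1.1), uneven application is foreseeable.

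**Working it through.** No figure in the plan is at issue, so the check sets the two lists side by side for an indeterminate screening result and runs test subjects through both.

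| Condition | Criterion 12 (Section 4.1.3) | Section 4.3.4.1 |
|---|---|---|
| Active TB history | Excluded | Excluded |
| Symptoms | None | None |
| Latent TB history | No condition | None, unless diagnosed within 3 years before screening and completed treatment is documented |
| Exposure | None known since last prophylaxis | No recent contact; the term is not defined |
| Chest film | Clear, within 3 months before first dose | Clear; no window stated |
| Repeat QFT-G | Weeks 12, 28, 40, 52 | Weeks 12, 28, 40, 52 |

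**Subject 1: latent TB history.** Indeterminate result; latent TB diagnosed and treated 5 years before screening; never active TB; no symptoms; no exposure since prophylaxis; clear film within 3 months of first dose. All three conditions of criterion 12 are met, so it admits the subject. In Section 4.3.4.1 the exception covers diagnoses within 3 years; 5 is greater than 3, so the history condition fails. The answers are opposite.

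**Subject 2: exposure without prophylaxis.** Indeterminate result; a known contact many years ago; prophylaxis never given, which criterion 12 permits because it requires prophylaxis only for a positive result. Criterion 12 counts exposure from the last prophylaxis, so here the interval has no starting point. A site could read this as any lifetime exposure (refuse) or as nothing to count (admit). Section 4.3.4.1 turns on whether the contact was recent, which it does not define. Neither passage gives a determinate answer.

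**Subject 3: control.** Indeterminate result; no TB history, symptoms or contact; clear film within 3 months. Both passages admit this subject, so an indeterminate result alone does not produce a conflict.

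**Subject 4: positive screening result.** Prophylaxis given and all three conditions met. Criterion 12 admits the subject; Section 4.3.4.1 says nothing about a positive result at screening.

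**Subject 5: older film.** Indeterminate result; the only clear film was taken more than 3 months before first dose. Criterion 12 refuses. Section 4.3.4.1 states no window and does not waive the one in criterion 12.

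Subject 1 shows a contradiction, Subject 2 two different and incomplete exposure tests, and Subjects 4 and 5 only silence in Section 4.3.4.1.

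**The case against.** The strongest reply is that eligibility is governed by the inclusion and exclusion criteria. Section 4.1.4 says that subjects who fail them should not be randomized, so a procedures section that grants permission cannot override criterion 12. On that reading a missing radiograph window in Section 4.3.4.1 changes nothing, because the 3-month window still binds, and a positive screening result is handled by criterion 12 alone. That reply stands for both points. A reader might infer that Section 4.3.4.1 bars subjects with a positive result; it does not say so.

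The reply does not settle the latent TB condition. There Section 4.3.4.1 adds a requirement that criterion 12 lacks, and nothing says whether it is an additional bar or whether criterion 12 is exhaustive. Specialist consultation may soften the problem in single cases, but it is optional and does not say which list applies.

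Two further inferences are tempting and unsupported:

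- **Forced discontinuations.** Section 4.1.6, item 3, stops dosing in subjects found after randomization to have met a safety-related exclusion criterion. Subject 1 satisfies criterion 12, and Section 4.3.4.1 is not an exclusion criterion, so the item does not reach this subject.
- **Everyone with a positive or indeterminate result is affected.** Subject 3 passes both lists. Applying an assumed rate of such results to the 552 planned subjects would count many who face no conflict, and would carry a rate among screened subjects over to randomized ones.

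**Conclusion.** The point holds for subjects with an indeterminate screening QFT-G. The two passages conflict on latent TB history, and their exposure conditions differ and are incompletely defined. The clear conflict is confined to otherwise qualifying subjects whose latent TB falls outside the 3-year and documentation exception. The exposure problem concerns subjects with a known past contact.

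The documents give neither the frequency of indeterminate results nor that of latent TB history, so the number affected cannot be derived. The conclusion does not depend on it: it rests on the current wording of both sections and on reading each list as written. This is an internal inconsistency about who may be randomized on a safety criterion. It does not alter the endpoints, the primary analysis or the sample size.

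**What to change.** Reconcile the two passages into a single set of entry conditions in criterion 12. Replace the restated conditions in Section 4.3.4.1 with a reference to that criterion, and send sites a clarification. The reconciled text should settle whether a latent TB history condition applies to an indeterminate result, and from what date or over what period exposure is counted, including for a subject never given prophylaxis. It would also be a convenient place to close the gap on positive screening results. The content of each condition, and whether it is the same for positive and indeterminate results, is for the sponsor's clinical team.

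The repeat-testing footnotes need no change. The cost is wording in two sections and one site communication, with no added procedures or subjects.
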